6.1 Study Design

AeroComp is service evaluation exploring the incidence of airway complications amongst patients undergoing general anaesthesia for surgical procedures within NHS Trusts. All adult patients undergoing any surgical procedure (with the exception of obstetric procedures) with the primary method of anaesthesia planned to be general anaesthesia will be eligible for enrolment to this study. The study duration will encompass 5 days (patients being enrolled over a 96 hour consecutive window with a further day of follow-up data collection) with an estimated total of 3600 patients being included. Individual sites are free to choose their own data collection window between 1st November

2021 and 3rd December 2021 as long as the 96 hour window commences at 07:30 on a Monday and closes at 07:29 on a Friday.

Primary outcome:

 Incidence of airway complications at both induction and emergence, defined as a composite of: airway trauma, aspiration, dental/lip/mucosal injury, change of intubation device, desaturation, three or more laryngoscopy attempts, grade 3 or 4 laryngoscopy, difficult face mask ventilation, difficult supraglottic airway device (SAD) usage, emergency front-of-neck airway, failed tracheal intubation, laryngospasm, oesophageal intubation (immediate or delayed recognition), requirement of reintubation immediately after extubation, and need for second intubator.

Secondary outcomes:

- Risk of composite outcome of airway complications will be reported for each individual component of the aerosol precaution bundle.
- Individual complications that comprise the primary outcome.
- Subjective operator assessment of airway difficulty
- Unanticipated airway difficulties necessitating significant deviation from the original airway plan.
- Composite risk of airway complication and association with confirmed/suspected COVID-19 infection, known negative COVID-19 infection without any potential COVID-19 risks, and all other patients.

7 List selection

Operating lists from all participating NHS hospitals will be included, with patients from those lists being eligible. Both elective and emergency cases will be included. The centres and local investigators will be identified by the Pan-London Perioperative Audit and Research Network (PLAN) or other national trainee research networks.

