 - Airway devices utilised: facemask, supraglottic airway device; tracheal tube; other (including rigid bronchoscope, jet ventilator and transnasal humidified rapid-insufflation ventilatory exchange)
 - Airway techniques including: direct laryngoscopy; videolaryngoscopy; use of a flexible bronchoscope over which a tracheal tube is passed, categorised into whether performed awake or asleep
 - Use of cricoid force?

- Adjunct equipment including: bougie; stylet; Oxford or HELP pillow; high and lowflow nasal cannulae; aerosol boxes or drapes; as well as a free text option for other potential equipment

- Patient COVID-19 status:
 - Positive: RT-PCR or lateral flow test positive for SARS-CoV-2; OR symptoms consistent with COVID-19 with no SARS-CoV-2 test available; OR recent exposure to SARS-CoV-2
 - Negative: RT-PCR or lateral flow test negative for SARS-CoV-2 infection; AND actively cohorted with other COVID-19 negative patients for the entirety of their hospital stay prior to this operation; AND self-isolated according to institutional guidelines.
 - Unclear: No SARS-CoV-2 result available with no risk factors; OR not self-isolated according to institutional guidelines; OR not in a COVID-19-free pathway.
- Whether anaesthesia was terminated at the end of the procedure with a plan to wake up the patient (emergence from anaesthesia).

Airway complications:

- Number of tracheal intubation attempts.
 An attempt is defined by the number of times the laryngoscopy device is inserted or reinserted into the patient's airway.
- Best grade of laryngoscopy: modified Cormack and Lehane grading [9] into 1, 2a, 2b, 3 and 4.
- The following complications categorised into induction and emergence (defined as the period around the time of cessation of anaesthesia until hand over of patient to recovery/intensive care staff):
 - Airway trauma: evidence of airway bleeding or oedema.
 - Dental injury (arising solely from anaesthetic, rather than surgical, interventions)
 - Lip and mucosal injuries (arising solely from anaesthetic, rather than surgical, interventions)
 - Pulmonary aspiration: inhalation of oropharyngeal or gastric contents into the larynx and lower respiratory tract [10]
 - Change of intubation device: use of an additional airway device, e.g. change from supraglottic airway to tracheal tube, change from direct to videolaryngoscopy (or vice versa), use of bougie if not initially anticipated, change in type of laryngoscope e.g. McCoy vs Macintosh blade

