15.2 Appendix 2 – Sample Case Record Form (CRF)

AER	COMP	Study Day ¹ : D Monda	, ,	Study ID: Hospital	:	
PATIENT DETAILS		PATIENT COVID-19 STATUS		SURGICAL DETAILS		
Age: 18 to 60 to Sex: Male Fema Other	79 🗖 80 and over	 Positive (PCR/LFT positive; CC Negative (PCR/LFT negative a COVID-19 free pathway) 	WID-19 symptoms; recent exposure) nd self-isolated and cohorted in	Surgical urgency ² :	Severity ³ : D Mind D Inter D Majo	rmediate
ASA Score:	− 29.9 □ 30.0 − 34.9	Unclear (No test result availal isolated; not cohorted in COVID-		Specialty: Breast ENT Bariatric General Cardiac Gynaecology Cardiology Max-Fax Dental Neurosurgery Other:	 Ophthalmology Ortho/Trauma Plastics Radiology Thoracic 	TransplantUrologyVascular
ANAESTHETIC DETA				Procedure performed within main operating theat	re complex: D Yes	No
Start time ^{1,4} : Grade of initial airway manager ⁵ : PPE worn by anaest Eye protection:	 00:00 to 07:29 07:30 tilde CT1-2 ST5-7 Consultion CT/ST3-4 SAS/SCF Other Other 07:30 tilde 07:30 ti	Itant Grade of second her airway manager ^{5,6} :	5 B	AIRWAY COMPLICATIONS (tick all that apply) Tracheal intubation attempts ⁸ : 1 2 Best grade of laryngoscopy ⁸ : 1 2 Was the patient woken up at the end of surgery? ⁹	□ 3 □ >3 □ 2b □ 3 □ Yes □ No	□ 4
Respiratory	 Other Surgical face mask 		Hazmat suitOther	Airway complications: (tick all that apply)	Induction	Emergence ⁹
rotection:	 Disposable FFP2/3 respirator Re-usable FFP2/3 respirator Powered air purifying respira Other 		 Single pair of gloves Double pair of gloves Other 	Airway trauma Aspiration Change of intubation device Death ¹⁰		
IRWAY MANAGEN Induction:	MENT (tick all that apply) Inhalational Intravenous: non-RSI	Equipment:	Bougie Stylet Cofeed pillour	Dental injury Desaturation (SpO₂ ≤90%) Desaturation (SpO₂ ≤80%) Difficult mask ventilation (2-person technique)		
Dxygenation:	 Intravenous: RSI/modified RS Pre-oxygenation Post-induction mask ventilati Apnoeic oxygenation 	ion	 Oxford pillow High-flow nasal cannulae Low-flow nasal cannulae Clear plastic 'aerosol' box Other 	Difficult SAD (excessive leak, poor ventilation, hypo Emergency front-of-neck airway Failed tracheal intubation – continue with SAD		
Airway device:	 Face mask (as sole airway de Supraglottic airway device Tracheal tube Other⁷ 	Airway technique: Direct laryngoscopy Video laryngoscopy Flexible bronchosco		Failed tracheal intubation – awaken patient Laryngospasm not reversed with positive pressure Lip/mucosal injury	D	

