- 6) Second airway manager: if a second individual took over management of the airway following management by the initial airway manager their grade should be recorded here and "second airway manager required" ticked within the complication section. Leave blank if not applicable.
- 7) Other: this applies to, for example, rigid bronchoscopes, jet ventilators and transnasal humidified rapid-insufflation ventilatory exchange. This should be ticked only if it was the primary airway device following induction of anaesthesia. Typically this will be a planned technique involving pre- +/- per-oxygenation following discussion with the operating surgeon beforehand. Also select if the primary means of oxygenation during the procedure is via a surgically placed jet ventilator (e.g. laryngeal procedures) and no other airway device is placed prior or subsequently by the anaesthetist. The exact device used does not have to be specified.
- 8) Tracheal intubation attempts/laryngoscopy grade should be left blank if intubation is not attempted. The grade here refers to the Cormack and Lehane system as modified by Yentis and Lee, shown below.
- 9) If the patient was not woken up at the end of surgery, emergence complications should not be recorded. If the patient was woken up and then immediately reintubated, this should be recorded as: Woken up: Yes; Reintubation immediately post-procedure: On emergence.
- 10) Only death due to hypoxia or another complication of airway management should be recorded.
- 11) Recognised oesophageal intubation is detected after the first but before the fourth ventilatory breath has been delivered. Delayed recognition is when four or more ventilatory breaths have been delivered.

	1	2		3	
Original Cormack and Lehane system	Full view of the glottis	Partial view of the glottis or arytenoids		Only epiglottis visible	Neither glottis nor epiglottis visible
View at laryngoscopy	E	Y	Y		
Modified system	1 As for original Cormack and Lehane above	2a Partial view of the glottis	2b Arytenoids or posterior part of the vocal cords only just visible	3 As for original Cormack and Lehane above	4 As for original Cormack and Lehane above

E = epiglottis, LI = laryngeal inlet. From Yentis SM, Lee DJH. (1998) Grading of direct laryngoscopy. Anesthesia. 53:1041-4.

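### The CRF opens the emergence column only if the patient was woken, while Section 9.1 defines emergence by the plan to wake, so complications in an abandoned wake-up can go unrecorded

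*Protocol*

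**What the plan says.** Section 6.1 defines the primary outcome as "Incidence of airway complications at both induction and emergence", a composite of listed complications. The individual complications are a secondary outcome.

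Section 9.1 lists a data item that defines emergence by intention: "Whether anaesthesia was terminated at the end of the procedure with a plan to wake up the patient". It sets the emergence period separately: "defined as the period around the time of cessation of anaesthesia until hand over of patient to recovery/intensive care staff". Neither statement requires that the patient actually woke.

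The CRF in Appendix 2 asks a different question: "Was the patient woken up at the end of surgery", answered Yes or No. Note 9 to the CRF makes the answer decide whether the emergence column may be used: "If the patient was not woken up at the end of surgery, emergence complications should not be recorded". The note then settles one special case: "If the patient was woken up and then immediately reintubated, this should be recorded as: Woken up: Yes", with the reintubation entered on emergence.

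**The concern.** Section 9.1 uses a plan; the CRF and note 9 use a result. The two part company when the result is itself produced by the event being measured. If anaesthesia is stopped with a plan to wake, an airway complication follows, and the attempt is given up before the patient wakes, Section 9.1 places the complication within emergence. Note 9, taken at its word, bars it from the form.

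Whether an event may be recorded then depends on the event. Any loss lowers the recorded rates and falls on complications serious enough to prevent waking. The individual complication rates are exposed first. The composite is exposed only for patients with no induction complication. Section 10.1 justifies the expected 3600 patients partly by the detection of rare events, so the rare severe components are where a few lost cases would be felt.

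**Working it through.** **1. The passages side by side**

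| Situation | Section 9.1 | CRF item and note 9, read literally |
|---|---|---|
| No wake-up planned | Not emergence | No; column blank |
| Woken, no reintubation | Emergence; events count | Yes; events recorded |
| Woken, then immediately reintubated | Emergence; events count | Yes; recorded on emergence (second sentence of note 9) |
| Wake-up planned and started, abandoned before waking because of an airway complication | Emergence; event falls within the window | No; event not recorded |

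Only the last row conflicts. The complication grid has two columns, induction and emergence, so an event barred from the second has no other correct place. The separate item on significant deviation from the airway plan is not part of the composite.

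**2. The plan's own figures**

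Inputs from Section 10.1 and Appendix 4: p = 0.05, d = 0.01, N = 1,000,000, Z = 1.96, design effect 1.

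n = N·p(1−p) / [(d²/Z²)(N−1) + p(1−p)] = 47,500 / (26.031 + 0.0475) = 1821.4, rounded up to 1822. This matches. The expected recruitment also matches: 50 centres × 18 procedures × 4 days = 3600. Neither figure is affected by this point; they only give the scale.

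**3. Scale for the composite**

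- Expected events at 5%: 3600 × 0.05 = 180.
- Each patient lost from the composite: 1/3600 = 0.028 percentage points.
- 95% half-width at 3600: 1.96 × √(0.05 × 0.95 / 3600) = 0.0071, or ±0.71 points.
- Losses needed to equal that half-width: 0.00712 × 3600 = 25.6, about 26 patients.

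**4. How many might be lost**

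The protocol gives no number of abandoned wake-ups. The three rates below are assumptions.

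- 95% of patients have a planned wake-up: 3600 × 0.95 = 3420.
- 2% of these have an emergence complication: 3420 × 0.02 = 68.
- 3% to 10% of those end in an abandoned wake-up: 68 × 0.03 = 2 and 68 × 0.10 = 7.
- Effect on the composite if none had an induction complication: 2/3600 = 0.06 points to 7/3600 = 0.19 points. A true 5% would be recorded as 178/3600 = 4.94% to 173/3600 = 4.81%.

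**5. Wider sensitivity**

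| Patients lost | Recorded incidence (true 5%) | Share of the 180 events |
|---|---|---|
| 4 | 4.89% | 2.2% |
| 9 | 4.75% | 5% |
| 18 | 4.50% | 10% |
| 36 | 4.00% | 20% |

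On the step 4 assumptions, reaching 26 losses would require 26/68 = 38% of emergence complications to end in an abandoned wake-up.

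**The case against.** The best defence is that the tick-box is shorthand for the Section 9.1 item and that note 9 is aimed at patients kept anaesthetised by plan. Its second sentence shows that a wake-up ending in reintubation is meant to be captured. The mention of intensive care staff in the hand-over window does not settle the matter, because woken patients also go to intensive care. This defence stands in part: some sites may read the form that way, so loss is not certain in every case. But neither the item nor the note says so, and the special case covers only patients who did wake. Sites that read it differently would code the same patient differently, which is a measurement fault in itself.

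Three stronger readings are tempting, and the document does not support them.

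- A reader might infer that every failed wake-up disappears from the primary outcome. It does not: patients woken and then reintubated are kept, and a patient with an induction complication still counts in the composite.
- A reader might add the patient whose intubation failed and whose surgery was abandoned. Failed intubation is a component of the composite with its own CRF line for awakening the patient, so that patient already counts. Section 9.1 also speaks of the end of the procedure and shares the same literal gap, so this is not a conflict between the two passages.
- A reader might claim damage to an emergence denominator or to a database skip rule. The protocol specifies neither: Section 10.2 reports the composite over the sampled population, and Section 9.1 mentions only data validation such as range checks.

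**Conclusion.** The conflict is real but narrow. It affects patients whose planned wake-up was started and then abandoned before waking because of an airway complication, at sites that follow note 9 literally. Their emergence complications are lost from the component rates, and from the composite when there was no induction complication. The direction is downward and the loss depends on the outcome.

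The number affected is unknown. The 2 to 7 patients (0.06 to 0.19 points) rest on assumed rates and on none of them having an induction complication. That is well inside the ±0.71 points of sampling error and the ±1 point target, so the conclusion on the primary outcome would not change. For rare severe components a few missing cases could matter, but the document gives no figure from which to size that, and a claim that a large share of severe emergence events is lost would go beyond it.

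**What to change.** Reconcile Section 9.1, the CRF item and note 9 so that all three rest on the plan to wake.

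- CRF item: *Was anaesthesia terminated with a plan to wake the patient? Yes/No.*
- Note 9, first sentence: *Leave the emergence column blank only if no wake-up was planned; if waking was started but abandoned, answer Yes and record all emergence complications.*
- Note 9, second sentence: keep the instruction for patients woken and then immediately reintubated, with its answer matched to the reworded item.

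The cost is rewording one item and one note on the paper form and in the electronic copy. No data item is added, and the sample size is unchanged.

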9.1 Data to be collected

Data will be collected on all operating lists with patients who meet inclusion criteria in participating hospitals. Each hospital taking part will have nominated staff who will be responsible for data collection.

For each day of the study the local investigating team will determine the total number of patients eligible for inclusion.

For each included patient, the anaesthetist or anaesthetic assistant (e.g. operating department practitioner, anaesthetic nurse) will be asked to complete a paper case record form (CRF; *Appendix* 2). Where more than one anaesthetist is involved, the most senior anaesthetist should be asked to complete the CRF.

Completed CRFs will be collected from the treating anaesthetic team. Local investigators will be responsible for ensuring accuracy and completeness of data. Where appropriate, this should include cross-checking with patient notes and other sources of information.

Completed CRFs will be stored in a secure location accessible by the local PI and other named members of the study team in accordance with NHS Information Governance standards. Information from each paper CRF, as well as the total number of eligible patients for each day of the project, will be entered via a secure web-based portal onto a secure database. The database will have data validation rules built-in to ensure accurate data entry (e.g. range checks, and field validation).

No patient-identifiable information will be uploaded to the secure database. Each site may elect to use a local ID upon the CRF to facilitate retrospective data capture within the immediate time frame of the project however this should be detached once the CRF is completed and will not form part of the dataset uploaded to the data capture server. Paper CRFs will be retained by the local study team in a locked, secure location in the hospital for a period of 6 months after the project ends to allow queries about study quality to be addressed during data cleaning and analysis. The local ID will not remain upon the CRF during this period.

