 - Desaturation: reduction in oxygen saturations to ≤90% during airway management
 - Severe Desaturation: reduction in oxygen saturations to ≤80% during airway management
 - Difficult mask ventilation: need for two-person (or more) mask ventilation
 - Difficult SAD insertion: multiple insertion attempts; excessive leak; insufficient ventilation; change of SAD size/design

- Failed tracheal intubation even after intervention of a second airway manager, including:

- If oxygenation and provision of anaesthesia was possible via SAD and a decision was made to continue with surgery

- If a decision was made to wake the patient and abandon surgery
- If this resulted in death this should be recorded separately, as above
- Laryngospasm: unwanted muscular response of the larynx that produces partial or complete obstruction of the laryngeal airway [11].
- Oesophageal intubation (recognised): tracheal tube placed in the oesophagus and recognised before delivery of the fourth ventilatory breath
- Oesophageal intubation (delayed recognition): tracheal tube placed in the oesophagus and 4 or more ventilatory breaths delivered.
- Reintubation within 30 minutes of the end of the procedure
- Second airway manager: initial airway manager either requests the assistance of a second individual to directly manage the airway or the supervising anaesthetist requests a second individual to take over management of the airway.
- Emergency front-of-neck airway
- Death due to hypoxia or other complication of airway management.
- Significant deviation from original airway plan
- Subjective assessment of ease of 1) mask ventilation, 2) SAD placement and use, and
 3) tracheal intubation, using a 5-point Likert scale (1-5) with addition of "not attempted" for each question

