Shaw *et al.* [12] reported an incidence of 91 airway complications in 1874 patients (~5%). Therefore, assuming an anticipated 5% incidence of our primary outcome in our study population, a desired error of +/-1% (absolute error) of our estimate for the incidence, and a 95% confidence level of achieving the desired estimate precision, we calculate the sample size required for our study to be \geq 1822 patients (Appendix 4; [13]). For a conservative estimate, with 50 centres each performing 18 procedures a day, we expect 3600 patients to be included, allowing acceptable rates of detection of rare events.

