10.2 Statistical analysis

Incidence of airway complications amongst the sampled population will be reported as a composite of airway complications as mentioned in **Section 9**.

Continuous data will be reported using means (standard deviation, SD) or medians (interquartile ranges [range]) where appropriate. Categorical data will be reported as numbers (percentages, %) with 95% confidence intervals (CI) calculated using an appropriate method, where applicable. A p value of < 0.05 will be considered as statistically significant. Relationships between categorical variables and outcome measures will be presented as univariate odds ratios with accompanying p-values (Pearson's Chi-square test with Yates' continuity correction). Univariable logistic regression models will be fitted to investigate potential associations between variables describing patient, operator or procedural characteristics and the primary outcome of incidence of airway complications. A multivariable logistic regression model will then be fitted to include all covariates to obtain adjusted association estimates. Variables included in the regression modelling will be selected based on scientific and clinical plausibility of affecting the outcome of airway management.

11 Ethical considerations

This study is designed as a service evaluation, and no ethical approval is expected to be required. As we are collecting routinely captured data with no patient identifiable data, and will not involve either direct patient contact or influence their care in any way, no patient consent will be required. Approval from the Caldicott Guardian at the lead site (Guy's and St. Thomas' NHS Foundation Trust, London, UK), and audit registration at all recruiting centres will be required prior to commencing the project. Participating hospitals will ensure that their local investigators will be appropriately trained, but no GCP certification will be required from investigating teams as this is a service evaluation. The local PI will ensure that no patient identifiable information will be stored during the study.

12 Financing and Insurance

No funding will be required for this study. All investigators will be NHS employees working in their respective trusts and standard NHS Indemnity will apply.

13 Reporting and dissemination

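### CRF note 11 sets a lower breath limit on recognised oesophageal intubation that Section 9.1 does not, so placements recognised before any breath may go unrecorded

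*Protocol*

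**What the plan says.** Section 6.1 lists "oesophageal intubation (immediate or delayed recognition") among the components of the primary composite. Section 10.2 says incidence will be "reported as a composite of airway complications as mentioned in" Section 9, so the Section 9.1 definitions govern the analysis.

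Section 9.1 has two categories. Recognised: "tracheal tube placed in the oesophagus and recognised before delivery of the fourth ventilatory breath". Delayed: "tracheal tube placed in the oesophagus and 4 or more ventilatory breaths delivered".

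The data come from the form. Section 9.1 states that the anaesthetist or anaesthetic assistant "will be asked to complete a paper case record form (CRF"). On that form both oesophageal tick boxes carry a pointer to note 11, which reads: "Recognised oesophageal intubation is detected after the first but before the fourth ventilatory breath has been delivered". It continues: "Delayed recognition is when four or more ventilatory breaths have been delivered".

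Individual complications are a secondary outcome in Section 6.1 and in the synopsis. All of this is current v1.2 text.

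**The concern.** The form is completed under one rule and the results are to be reported under another. The delayed category is the same in both places. The recognised category is not: the form adds a lower limit that Section 9.1 lacks. The cases left out are those recognised earliest.

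Two results are exposed. The count for the individual oesophageal component would be too low. The split between recognised and delayed would tilt towards delayed, because any loss falls only on the recognised side. The primary composite is exposed to a lesser degree, because a patient can enter it through many other components.

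**Working it through.** **Step 1. The definitions by number of breaths given before recognition.**

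| Breaths | Section 9.1 | CRF note 11 |
|---|---|---|
| 0 | recognised | neither category |
| 1, 2 or 3 | recognised | recognised |
| 4 or more | delayed | delayed |

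Section 9.1 places every case. Note 11, read literally, leaves the zero-breath row without a box.

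**Step 2. Can such a patient be event-free on the form?** Yes. Section 9.1 counts an attempt each time the laryngoscopy device is inserted or reinserted. A tube withdrawn and re-passed after one reinsertion gives two attempts, below the composite's threshold of three. With the same device, the same operator, a grade 1 or 2 view and no desaturation or injury, nothing else need be ticked. That patient has the primary outcome under Section 9.1 and none on the form. If any other component is ticked, the patient stays in the composite and only the oesophageal component loses the case.

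**Step 3. The plan's own figures.** With p = 0.05, d = 0.01, N = 1,000,000, DEFF = 1 and Z = 1.96, the Appendix 4 equation gives n = 1821.4, rounded up to 1822, as stated. Expected accrual is 50 × 18 × 4 = 3600, also as stated. Neither depends on note 11. At 3600 patients the 95% half-width is 1.96 × √(0.05 × 0.95 / 3600) = 0.0071, or 0.71 percentage points.

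**Step 4. Size of the loss.** Let r be the proportion of all patients with a zero-breath placement left unticked, and u the share of those with no other component. The component loses 3600 × r patients. The composite loses 3600 × r × u patients, or 100 × r × u percentage points. The protocol gives neither r nor u.

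*Illustration; every input is an assumption.* Take 2000 intubations, oesophageal placement in 0.5% to 1%, and 25% to 50% of those recognised before any breath and left unticked.

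- Low: 2000 × 0.005 × 0.25 = 2.5 patients; 2.5 / 3600 = 0.07 points.
- High: 2000 × 0.01 × 0.50 = 10 patients; 10 / 3600 = 0.28 points.

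These are ceilings for the composite under those inputs, because they set u = 1. With u = 0.25 the range is 0.02 to 0.07 points.

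*Wider range, also assumed.* With r from 0.1% to 1% and u from 25% to 100%, the loss runs from 0.9 to 36 patients, and a true 5% would read as 4.98% to 4.0%.

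*What a material shift would take.* A 1-point shift needs 0.01 × 3600 = 36 patients. At 5% incidence, 0.05 × 3600 = 180 events are expected, so 36 / 180 = 20% of all primary events would have to be unticked zero-breath placements with nothing else recorded.

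**Step 5. The recognised/delayed split (illustration).** Suppose 10 placements, 2 of them delayed: a true delayed share of 2/10 = 20%. If 25% of the 10 are lost, all from the recognised side, the share becomes 2/7.5 = 27%. If 50% are lost, it becomes 2/5 = 40%.

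**The case against.** The difference in wording cannot be argued away, but its consequences can be overstated in several ways.

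- **Loss from the composite.** A reader might infer that every zero-breath placement drops out of the primary outcome. The documents do not support that. The composite in Section 6.1 is broad, and a change of device under Section 9.1 includes an unanticipated bougie or a different laryngoscope blade, both plausible after a misplaced tube. Only patients with no other component are lost. This part of the objection stands in full.
- **Certainty of loss.** The tick box itself says only that the intubation was recognised; the lower limit sits in a numbered note. Some clinicians will tick it for a zero-breath placement anyway. Section 9.1 also makes local investigators responsible for accuracy and completeness, with cross-checking against notes where appropriate. So loss is possible, not certain. But if some follow the note and others do not, the component is recorded under mixed rules, which is still a defect.
- **Section 6.1 as proof.** It is tempting to read immediate recognition there as meaning before any breath. The term is undefined and may simply contrast with delayed. The contradiction rests on Section 9.1 against note 11, and is sufficient on that basis.
- **A doubled delayed share.** The move from 20% to 40% comes only from the top of an assumed range; at the bottom it is 27%. It shows direction, not size.

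**Conclusion.** The contradiction holds as written: note 11 requires detection after the first breath, and Section 9.1 does not. Followed literally, note 11 loses zero-breath placements from the individual oesophageal component in every case, and from the primary composite only where no other component is ticked.

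The number of patients cannot be derived from the documents. Under the narrower assumed inputs above, the composite would lose at most 0.07 to 0.28 points, against a target precision of ±1 point. A loss as large as 1 point would need a fifth of all expected primary events to be of this kind, and nothing in the protocol suggests that. The effect on the headline incidence is therefore probably small. The effect on the oesophageal component and its recognised/delayed split could be proportionately larger, but is equally unquantified. The sample size of 1822 is untouched. This is a minor inconsistency in a recording definition, worth correcting because correction is nearly free.

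**What to change.** Reconcile note 11 with Section 9.1 so that recognised means detected at any time before the fourth ventilatory breath, including before any breath is given. If the eCRF carries matching help text, which is not shown in the protocol, change it in the same way. The cost is a few words in one note, with no added data items or staff time.

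If data are already collected, state in the report that the CRF note and the protocol definition differed, and that capture of zero-breath placements is uncertain and may be incomplete. Do not relabel the component as recognised after at least one breath: the box label has no lower limit, so ticked cases may include zero-breath placements and that label could be false. Going back to the notes is unlikely to settle it, because Section 9.1 has any local ID detached once the form is completed.
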